10.4 Drug accountability

The study drug provided for this study will be used only as directed in the study protocol.

The study personnel will account for all study drugs dispensed to and returned from the healthy volunteer.

At the end of the study, study site personnel will account for all study drugs received at the site, unused study drugs and for appropriate destruction. Destruction must not take place unless the Sponsor has approved it. Certificates of delivery and destruction must be signed. The investigator is responsible for ensuring that dosing is administered in compliance with the protocol. Delegation of this task must be clearly documented and approved by the investigator. All study drug administration will occur under medical supervision.

10.5 Treatment assignment and blinding

10.5.1 Randomization and treatment assignment

This is a non-randomized study.

If a subject, who does not meet the selection criteria, has been dosed before the error is identified, the subject should be advised to continue safety assessments to ensure their safety. The investigator will inform the Sponsor of the error and a joint decision made as to whether the subject should be replaced.

10.5.2 Blinding

This is an open label study

10.6 Dosing Procedure

After an overnight fasting of at least 10 hours, the IMP will be administered to the subjects according to the dosing schedule for the cohort they are part of.

Dosing of the subjects will be conducted in the following manner: subjects will be dosed one by one in a designated room. Prior to each subject being invited to the dosing room, the PI and a designated study nurse will check the prepared IMP in accordance with the relevant dosing scheme. Upon subject's entry in the dosing room, the subject's number will be crosschecked with the IMP that is prepared and with the dosing scheme again. Upon confirmation by the PI and the study nurse that the IMP is the right one and can be administered, the PI will perform the administration according to the available instructions. The Investigator will also perform a visual IMP identity and intactness check of the IMP prior to the administration. In case of an incorrect identity or damaged tablet, the IMP will be replaced with a correct identity or undamaged tablet. IMP will be administered orally to each subject in an upright position. IMP

administration of the tablet will be done by a dispensation spoon followed by intake of 240 mL water as described in sections 10.6.1 – 10.6.3.

After the IMP was administered the PI will check the subject's oral cavity by looking under the tongue, under the lips, in the corners of the mouth and between gums and cheeks, using a tongue depressor or a spatula. In case of the Test IMP the PI will confirm that the subject had swallowed the administered dose.

Drug accountability and dispensing records will be maintained at all times. Each activity including date and time of each dose will be documented at the time it is performed in the source documentation. Copy of labels will be stuck in the source documentation at the time of dosing. All empty IMP containers/packaging will be stored in a secure area.

For each subject, all scheduled post dose activities and assessments will be performed relative to the time of study treatment administration.

For Test Product only the taste assessment will be done by the trained study personnel after dosing in each period and will be recorded in the source data form.

10.6.1 Benfo-oxythiamine (B-OT)

- Depending on the assigned dose, one or more than one tablet of the test product (benfo-oxythiamine (B-OT)) will be administered with 240 mL of water.

The tablet(s) must be swallowed whole. The tablet(s) must not be sucked, chewed or broken.

No water will be allowed one hour before and one hour after administration, except 240 mL of water administered together with benfo-oxythiamine (B-OT) administration.

10.7 Treatment Compliance

Administration of investigational products will only be performed by authorized clinical research staff and will be followed by a hand and oral cavity check in order to confirm the swallowing of the product and fluid intake, if applicable.

Upon dispensing medication, the clinical research staff will record the related information on the applicable source documents, to allow investigational product accountability and evaluation of subject compliance.

11 STUDY ENDPOINTS

11.1 Primary endpoints

The outcome measures for the safety endpoints of the study will be safety laboratory assessments, physical examination (PE), electrocardiograms (ECGs), vital signs, adverse events (AEs) and serious adverse events (SAEs).

The safety variables will mainly be addressed by the adverse events (AEs) data as determined by clinical or biochemical/ hematologic investigations.

The safety variables will be tabulated for all study participants. AE data will be processed in the statistical analysis after coding according to MedDRA dictionary. AEs will be presented in summary tables. These tables will show the number of subjects per group presenting an AE and the incidence of its occurrence. AEs will be grouped by system organ class and stratified by severity and by relation to study treatment.

Adverse events which will be summarized and will be categorized in subsets of all treatment-emergent AEs, and of all treatment-related AEs.

Clinical laboratory and vital signs will be summarized by change from baseline.

11.2 Secondary endpoints

In the SAD part of the study, the following PK endpoints will be derived from plasma benfoxythiamine (B-OT) and oxythiamine (OT) concentration versus time data following administration according to the dosing schedule: C_{max} , t_{max} , $t_{1/2}$, CL/F , λ_z , V_z/F , AUC_{0-inf} and AUC_{last} as appropriate.

In the MAD part of the study the following PK endpoints will be derived from plasma oxythiamine (OT) concentration versus time data following administration according to the dosing schedule on Day 1: AUC_{τ} , C_{max} , t_{max} , on Day 7: AUC_{τ} , $C_{max,ss}$, $t_{max,ss}$, $Swing$, $PTF\%$, CL_{ss}/F , V_z/F , C_{trough} , C_{av} , C_{min} , $t_{1/2}$, AUC_{inf} and AUC_{last} as appropriate and Day7/Day1: $Ra(AUC_{\tau})$, $Ra(C_{max})$.

11.3 Exploratory endpoints

- To evaluate the pharmacodynamics (PD) by measuring the transketolase activity.
- To analyse PK parameters of other B-OT derivative metabolite(s), if any.

12 STUDY ASSESSMENTS (SAD AND MAD)

12.1 Visit Procedures (SAD)

The procedures per visit to be performed in the SAD part of the study are listed below.

12.1.1 Procedures during the Screening Visit (Day -28 to -2)

- Subjects will come to the Clinical site for an ambulatory screening visit
- Subjects will be fully informed verbally and in writing about the study procedures and their responsibilities/rights while participating in the study
- If the subject agrees to participate in the study, he or she will sign a written informed consent
- Subjects will provide nasopharyngeal and oropharyngeal swab which will be tested for the presence of SARS-COV-2 (COVID – 19) infection with a rapid antigen test
- Subjects will be screened for inclusion and exclusion criteria
- The Investigator will record any prior and concomitant medical conditions/medications
- Subjects will provide a detailed medical history and demographic data
- Subjects will undergo a complete physical examination including documenting weight, height, BMI
- Subjects will have their vital signs (heart rate, blood pressure, respiratory rate, body temperature) recorded
- Subjects will undergo a breath alcohol test
- Subjects will provide blood and urine samples for laboratory analysis (biochemistry, hematology, serology, urinalysis); the urine sample will be used also for drug screen test and cotinine test performed via dip stick
- Subjects will undergo a 12-lead ECG
- The Investigator will record any AEs that have occurred during visit with the subject
- Eligible subjects will be invited for a treatment visit

Subjects who meet the inclusion and have no exclusion criteria will be scheduled to attend the treatment visit (Day -1 to Day 4).

The subjects will arrive at the study site in the morning of Day -1 for the conduct of the treatment visit, provided that they have had a negative Sars-CoV2 tests result from the morning of the same day or the evening of the previous one. In case this time frame cannot be respected, the time of testing will be decided on a case-by-case basis by the Sponsor, respecting the official validity period of the test which is 72 h.

12.1.2 Procedures on Day -1

- Subjects will provide nasopharyngeal and oropharyngeal swab which will be tested via PCR for the presence of SARS-COV-2 (COVID – 19) infection in the morning by visiting the laboratory point of testing indicated by the Investigator during the screening visit
- Subjects will arrive at the unit in the afternoon after a confirmed COVID-19 negative result is available from the laboratory
- Subjects' eligibility will be re-checked and medical history re-reviewed

- Subjects will undergo a complete physical examination including documenting weight
- The Investigator will review any AEs that have occurred since the previous visit with the subject
- Subjects will undergo a breath alcohol test
- Subjects will provide blood and urine samples for laboratory analysis (biochemistry, hematology, urinalysis); the urine sample will be used also for drug screen test and cotinine test performed via dip stick
- Subjects will have their vital signs measured
- The Investigator will record any changes in concomitant medications or illnesses with the subject since the last study visit
- Subjects will be admitted to the stationary unit of the site
- Subjects will receive unified balanced evening meal

12.1.3 Procedures on Day 1

- Subjects will be fasted from midnight (at least 10 hours fasting prior to dosing)
- Subjects will have their vital signs recorded (pre-dose and approximately 2, 4, 8, 12 hours after dosing)
- Subjects will undergo limited physical examination to target any change from the previous status or any body system deemed pertinent to that subject by the PI (or designee) 4 hours post dose
- Subjects will undergo a 12-lead ECG pre-dose
- Subjects will receive a single dose of the assigned IMP Benfo-oxythiamine (B-OT) between a time interval of two hours between 07:00 am and 09:00 am.
- Catheter for blood sampling will be inserted and serial blood samples will be collected for PK and PD analysis according to the sample schedule in section 12.4.1 Blood samples collection
- AEs that have occurred will be recorded
- Concomitant medication intake will be recorded
- Subjects will receive unified balanced lunch, afternoon snack and evening meal throughout the day

12.1.4 Procedures on Day 2

- Subjects will be fasted from midnight (at least 10 hours fasting prior to safety laboratory samples collection)
- Subjects will have their vital signs recorded
- Subjects will undergo limited physical examination to target any change from the previous status or any body system deemed pertinent to that subject by the PI (or designee)
- Subjects will provide blood and urine samples for laboratory analysis (biochemistry, hematology, urinalysis);
- Subjects will undergo a 12-lead ECG

- Blood samples will be collected for PK and PD analysis according to the sample schedule in section 12.4.1 Blood samples collection
- AEs that have occurred will be recorded
- Concomitant medication intake will be recorded
- Subjects will receive unified balanced lunch, afternoon snack and evening meal throughout the day

12.1.5 Procedures on Day 3

- Subjects will be fasted from midnight (at least 10 hours fasting prior to safety laboratory samples collection)
- Subjects will have their vital signs recorded
- Subjects will provide urine samples for laboratory urine analysis
- Blood samples will be collected for PK and PD analysis according to the sample schedule in section 12.4.1 Blood samples collection
- AEs that have occurred will be recorded
- Concomitant medication intake will be recorded
- Subjects will receive unified balanced lunch, afternoon snack and evening meal throughout the day

12.1.6 Procedures on Day 4

- Subjects will be fasted from midnight (at least 10 hours fasting prior to safety laboratory samples collection)
- Subjects will provide nasopharyngeal and oropharyngeal swab which will be tested via PCR for the presence of SARS-COV-2 (COVID – 19) infection
- Subjects will have their vital signs recorded
- Subjects will undergo limited physical examination to target any change from the previous status or any body system deemed pertinent to that subject by the PI (or designee)
- Subjects will provide blood and urine samples for laboratory analysis (biochemistry, hematology, urinalysis)
- Blood samples will be collected for PK and PD analysis according to the sample schedule in section 12.4.1 Blood samples collection
- AEs that have occurred will be recorded
- Concomitant medication intake will be recorded
- Subjects will be discharged from the Clinical site as soon as all scheduled procedures have been completed

12.1.7 Procedures on Follow-up visit (Day 8)

- Subjects will come to the Clinical site for an ambulatory End of study visit
- Subjects will undergo a complete physical examination including documenting weight
- Subjects will provide nasopharyngeal and oropharyngeal swab which will be tested for the presence of SARS-COV-2 (COVID – 19) infection with a rapid antigen test

- Subjects will have their vital signs (heart rate, blood pressure, respiratory rate, body temperature) recorded
- Subjects will undergo a 12-lead ECG
- Subjects will undergo a breath alcohol test
- Subjects will provide blood and urine samples for laboratory analysis (biochemistry, hematology, urinalysis); the urine sample will be used also for drug screen test and cotinine test performed via dip stick
- Blood samples will be collected for PK and PD analysis according to the sample schedule in section 12.4.1 Blood samples collection
- AEs that have occurred will be recorded
- Concomitant medication intake will be recorded
- Subjects will complete the study and their participation will be ended

See [Table 1](#) for the time points of all the assessments planned in the study.

12.2 Visit Procedures (MAD)

The procedures per visit to be performed in the MAD part of the study are listed below.

12.2.1 Procedures during the Screening Visit (Day -28 to -2)

- Subjects will come to the Clinical site for an ambulatory screening visit
- Subjects will be fully informed verbally and in writing about the study procedures and their responsibilities/rights while participating in the study
- If the subjects agree to participate in the study, they will sign a written informed consent
- Subjects will provide nasopharyngeal (through the nose) and/or oropharyngeal (through the mouth) swab which will be tested for the presence of SARS-COV-2 infection with a rapid antigen test
- Subjects will be screened for inclusion and exclusion criteria
- The Investigator will record any prior and concomitant medical conditions/medications
- Subjects will provide a detailed medical history and demographic data
- Subjects will undergo a complete physical examination including documenting weight, height, body mass index (BMI)
- Subjects will have their vital signs (heart rate, blood pressure, respiratory rate, body temperature) recorded
- Subjects will undergo a breath alcohol test
- Subjects will provide blood and urine samples for laboratory analysis (biochemistry, hematology, serology, urinalysis); the urine sample will be used also for drug screen test and cotinine test performed via dip stick
- Adverse events (AEs) that have occurred during the visit will be recorded
- Subjects will undergo a 12-lead ECG
- Subjects will be invited for a treatment visit

If Subjects fulfill the inclusion criteria and do not meet any exclusion criteria, Subjects will be scheduled to attend the treatment visit (Day -1 to Day 8).

Subjects will arrive at the study site in the afternoon of Day -1 for the conduct of the treatment visit

12.2.2 Procedures on Day -1

- Subjects will provide nasopharyngeal and/or oropharyngeal swab which will be tested for the presence of SARS-COV-2 infection with a rapid antigen test
- Subjects will arrive at the unit in the afternoon
- Subjects' eligibility will be re-checked and medical history re-reviewed
- Subjects will undergo a complete physical examination including documenting weight
- The Investigator will review any adverse events (AEs) that have occurred since the previous visit with the subjects
- Subjects will undergo a breath alcohol test
- Subjects will provide blood and urine samples for laboratory analysis (biochemistry, hematology, coagulation, urinalysis); the urine sample will be used also for drug screen test and cotinine test performed via dip stick
- Subjects will have their vital signs measured
- The Investigator will record any changes in concomitant medications or illnesses with the subjects since the last study visit
- Subjects will be admitted to the stationary unit of the site
- Subjects will receive unified balanced evening meal

12.2.3 Procedures on Day 1

- Subjects will be fasted from midnight (at least 10 hours fasting prior to dosing)
- Subjects will have their vital signs recorded (pre-dose)
- Subjects will undergo limited physical examination to target any change from the previous status or any body system deemed pertinent to Subjects by the PI (or designee) 4 hours post dose
- Subjects will undergo a 12-lead ECG pre-dose
- Subjects will receive a single dose of the assigned IMP (benfo-oxythiamine (B-OT)) within a time interval of two hours between 07:00 am and 09:00 am.
- Catheter for blood sampling will be inserted and serial blood samples will be collected for pharmacokinetic (PK) and pharmacodynamic (PD) analysis according to the sample schedule in section 12.4.1 Blood samples collection.
- Adverse events (AEs) that have occurred will be recorded
- Concomitant medication intake will be recorded
- Subjects will receive unified balanced lunch, afternoon snack and evening meal throughout the day

12.2.4 Procedures on Day 2

- Subjects will be fasted from midnight (at least 10 hours fasting prior to dosing)
- Subjects will have their vital signs recorded (pre-dose and approximately 4 hours after dosing)

- Subjects will undergo a limited physical examination to target any change from the previous status or any body system deemed pertinent to Subjects by the PI (or designee) 4 hours post dose
- Subjects will provide blood and urine samples for laboratory analysis (biochemistry, hematology, coagulation, urinalysis)
- Subjects will undergo a 12-lead ECG pre-dose
- Subjects will receive a single dose of the assigned IMP (Benfo-Oxythiamine (B-OT) within a time interval of two hours between 07:00 am and 09:00 am.
- Catheter for blood sampling will be inserted and serial blood samples will be collected for pharmacokinetic (PK) and pharmacodynamic (PD) analysis according to the sample schedule in section 12.4.1 Blood samples collection.
- Adverse events (AEs) that have occurred will be recorded
- Concomitant medication intake will be recorded
- Subjects will receive unified balanced lunch, afternoon snack and evening meal throughout the day

12.2.5 Procedures on Day 3

- Subjects will be fasted from midnight (at least 10 hours fasting prior to dosing)
- Subjects will have their vital signs recorded (pre-dose)
- Subjects will undergo a limited physical examination to target any change from the previous status or any body system deemed pertinent to Subjects by the PI (or designee) 4 hours post dose
- Subjects will receive a single dose of the assigned IMP (Benfo-Oxythiamine (B-OT) within a time interval of two hours between 07:00 am and 09:00 am.
- Catheter for blood sampling will be inserted and serial blood samples will be collected for pharmacokinetic (PK) analysis according to the sample schedule in section 12.4.1 Blood samples collection
- Adverse events (AEs) that have occurred will be recorded
- Concomitant medication intake will be recorded
- Subjects will receive unified balanced lunch, afternoon snack and evening meal throughout the day

12.2.6 Procedures on Day 4

- Subjects will be fasted from midnight (at least 10 hours fasting prior to dosing)
- Subjects will have their vital signs recorded (pre-dose)
- Subjects will undergo a limited physical examination to target any change from the previous status or any body system deemed pertinent to Subjects by the PI (or designee) 4 hours post dose
- Subjects body weight will be measured
- Subjects will undergo a 12-lead ECG pre-dose
- Subjects will receive a single dose of the assigned IMP (Benfo-Oxythiamine (B-OT) within a time interval of two hours between 07:00 am and 09:00 am.

- Catheter for blood sampling will be inserted and serial blood samples will be collected for pharmacokinetic (PK) and pharmacodynamic (PD) analysis according to the sample schedule in section 12.4.1 Blood samples collection
- Adverse events (AEs) that have occurred will be recorded
- Concomitant medication intake will be recorded
- Subjects will receive unified balanced lunch, afternoon snack and evening meal throughout the day

12.2.7 Procedures on Day 5

- Subjects will be fasted from midnight (at least 10 hours fasting prior to dosing)
- Subjects will have their vital signs recorded (pre-dose and approximately 4 hours after dosing)
- Subjects will undergo a limited physical examination to target any change from the previous status or any body system deemed pertinent to Subjects by the PI (or designee) 4 hours post dose
- Subjects will provide blood and urine samples for laboratory analysis (biochemistry, hematology, coagulation, urinalysis)
- Subjects will receive a single dose of the assigned IMP (Benfo-Oxythiamine (B-OT)) within a time interval of two hours between 07:00 am and 09:00 am.
- Catheter for blood sampling will be inserted and serial blood samples will be collected for pharmacokinetic (PK) and pharmacodynamic (PD) analysis according to the sample schedule in section 12.4.1 Blood samples collection
- Adverse events (AEs) that have occurred will be recorded
- Concomitant medication intake will be recorded
- Subjects will receive unified balanced lunch, afternoon snack and evening meal throughout the day

12.2.8 Procedures on Day 6

- Subjects will be fasted from midnight (at least 10 hours fasting prior to dosing)
- Subjects will have their vital signs recorded (pre-dose)
- Subjects will undergo a limited physical examination to target any change from the previous status or any body system deemed pertinent to Subjects by the PI (or designee) 4 hours post dose
- Subjects will receive a single dose of the assigned IMP (Benfo-Oxythiamine (B-OT)) within a time interval of two hours between 07:00 am and 09:00 am.
- Catheter for blood sampling will be inserted and serial blood samples will be collected for pharmacokinetic (PK) analysis according to the sample schedule in section 12.4.1 Blood samples collection
- Adverse events (AEs) that have occurred will be recorded
- Concomitant medication intake will be recorded
- Subjects will receive unified balanced lunch, afternoon snack and evening meal throughout the day

12.2.9 Procedures on Day 7

- Subjects will be fasted from midnight (at least 10 hours fasting prior to dosing)
- Subjects will have their vital signs recorded (pre-dose and approximately 4 hours after dosing)
- Subjects will undergo limited physical examination to target any change from the previous status or any body system deemed pertinent to Subjects by the PI (or designee) 4 hours post dose
- Subjects will undergo a 12-lead ECG pre-dose
- Subjects will receive a single dose of the assigned IMP (Benfo-Oxythiamine (B-OT) within a time interval of two hours between 07:00 am and 09:00 am.
- Catheter for blood sampling will be inserted and serial blood samples will be collected for pharmacokinetic (PK) and pharmacodynamic (PD) analysis according to the sample schedule in section 12.4.1 Blood samples collection
- Adverse events (AEs) that have occurred will be recorded
- Concomitant medication intake will be recorded
- Subjects will receive unified balanced lunch, afternoon snack and evening meal throughout the day

12.2.10 Procedures on Day 8

- Subjects will have their vital signs recorded
- Subjects will undergo a limited physical examination to target any change from the previous status or any body system deemed pertinent to Subjects by the PI (or designee)
- Subjects body weight will be measured
- Subjects will provide blood and urine samples for laboratory analysis (biochemistry, hematology, coagulation, urinalysis)
- Catheter for blood sampling will be inserted and serial blood samples will be collected for pharmacokinetic (PK) and pharmacodynamic (PD) analysis according to the sample schedule in section 12.4.1 Blood samples collection
- Adverse events (AEs) that have occurred will be recorded
- Concomitant medication intake will be recorded
- Subjects will receive unified balanced lunch, afternoon snack and evening meal throughout the day

12.2.11 Procedures on follow-up Day 11

- Subjects will have their vital signs recorded
- Subjects will undergo limited physical examination to target any change from the previous status or any body system deemed pertinent to Subjects by the PI (or designee)
- Subjects body weight will be measured
- Subjects will provide blood and urine samples for laboratory analysis (biochemistry, hematology, coagulation, urinalysis)

- Catheter for blood sampling will be inserted and serial blood samples will be collected for pharmacokinetic (PK) analysis according to the sample schedule in section 12.4.1 Blood samples collection
- Adverse events (AEs) that have occurred will be recorded
- Concomitant medication intake will be recorded

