Visit	Screening (Days -28 to -2)	Day -1	Day 1 (T=0)	Day 2 (24 hr) +/- 30min	Day 3 (48 hr) +/-1hr	Day 4 (72 hr) +/-1hr	Day 8 (EOS) (168 hr) +/-2hr	
Viral screening (HIV, Hepatitis)	x							
Drug screening	x	x					x	
Breath alcohol test	x	x					x	
Weight/height (BMI)	x	x ⁶					x ⁶	⁶ : only weight on Day -1 and 8
Confinement		x	x	x	x	x		
Ambulatory visit	x						x	
Administer study drug			x ⁷					⁷ : T=0 is time of drug administration
Plasma PK sample collection			x ⁸	x ⁹	x ⁹	x ⁹	x ⁹	⁸ : PK samples should be collected pre-dose and at 0.25, 0.5, 0.75, 1, 1.5, 2, 4, 8, 12 hr. depending on ongoing PK data review, timepoints may be modified or removed. ⁹ : PK samples should be collected at 24, 36, 48, 72 and 168 hr post-dose on Day 2, 3, 4 and 8
PD (TKT activity)			x ¹⁰	x	x	x	x	¹⁰ : on Day 1, TKT blood sample should be taken pre-dose and at 1, 2, 4, 8, and 12 hr and then at 24, 48, 72 and 168 hr post-dose.
Adverse Events	x ¹¹	x ¹¹	x ¹¹	x	x	x	x	¹¹ : Adverse events occurring prior to study drug administration should be recorded as medical history unless the event is directly related to study specific procedure
Prior and/or Concomitant medications	x	x	x	x	x	x	x	

CONFIDENTIAL

Study Protocol

Study number: BV-01-101

Version No. : 3.0

Date: 13 Jul 2022

TABLE 2: VISIT AND ASSESSMENT SCHEDULE OF THE MULTIPLE ASCENDING DOSE PART

Visit	Screening (Days -28 to -2)	Day -1	Day 1	Day 2	Day 3	Day 4	Day 5	Day 6	Day 7	Day 8	Day 11	Day 14 (EOS)	
Informed consent	x												
Demography	x												
I/E; Medical history	x	x											
Ambulatory visit	x										x	x	
Confinement		x	x	x	x	x	x	x	x	x			
Administer study drug			x	x	x	x	x	x	x				
Physical examination-PE ¹	x	x	x	x	x	x	x	x	x	x	x	x	¹ : a complete PE will be performed at Screening and/or Check-in and EOS; on all other days, a limited PE will target any change from the previous status, or any body system deemed pertinent to that subject by the PI (or designee)
Vital signs ²	x	x	x	x ³	x	x	x ³	x	x ³	x	x	x	² : vital signs include pulse rate, respiratory rate, blood pressure and body temperature; if not otherwise indicated, VS should be taken either at pre-dose on dosing days or at time of visit on ambulatory visit days ³ : on Day 2, 5 and 7, VS should be taken pre-dose and at 4 hr post-dose
Laboratory assessment (hematology, biochemistry, coagulation)	x	x ⁴		x ⁴			x ⁴			x	x	x	⁴ : Results for safety blood samples must be available and reviewed before drug is administered on Day 1, 3 and 6

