14.7 Baseline parameters

Baseline is defined as the last value prior to dosing. Change from baseline will be calculated for all continuous safety parameters.

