### 6.2 Demographics and baseline measurements

Baseline is defined as the last value prior to dosing. Absolute change from baseline will be calculated for all continuous safety parameters. Baseline demographic data will be tabulated and presented by dose.

Demographic data: age, height, weight and body mass index (BMI) will be summarized by descriptive statistics (n, mean, standard deviation, median, minimum and maximum), and gender and race, will be summarized by the number and percentage of subjects in each category in Table “*Demographics*”.

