#### Safety Data and Adverse events

Table II.14.3.1 Overall Incidence of Treatment Emergent Adverse Events

Table II.14.3.2 Treatment Emergent Adverse Events, by SOC and PT

Table II.14.3.3 Related Treatment Emergent Adverse Events, by SOC and PT

Table II.14.3.4 Treatment Emergent Serious Adverse Events, by SOC and PT

Table II.14.3.5 Summary of Hematology Parameters - Actual Values and Change from Baseline

Table II.14.3.6 Summary of Biochemistry Parameters - Actual Values and Change from Baseline

Table II.14.3.7 Summary of Urinalysis Parameters

Table II.14.3.81 Summary of Vital Signs: Actual Values and Change from Baseline

Table II.14.3.12 Overall ECG Assessment

Table II.14.3.13 Concomitant Therapy by ATC code (if appropriate)

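### In the MAD part the laboratory baseline is a Day -1 sample taken after afternoon arrival with no fast required, and later draws are not matched to it, so change in glucose and triglycerides can be confounded by meals and time of day

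*Protocol*

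**What the plan says.** **Baseline.** Protocol 14.7: "Baseline is defined as the last value prior to dosing". SAP 6.2 repeats this and adds: "Absolute change from baseline will be calculated for all continuous safety parameters". The SAP table lists for both parts include a "Summary of Biochemistry Parameters - Actual Values and Change from Baseline".

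**MAD schedule.** Protocol Table 2 places safety laboratory tests at Screening and on Days -1, 2, 5, 8, 11 and 14, with none on Day 1. Its footnote 4 reads: "Results for safety blood samples must be available and reviewed before drug is administered on Day 1, 3 and 6".

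**MAD Day -1 (protocol 12.2.2).** "Subjects will arrive at the unit in the afternoon"; 8.1 and 12.2.1 agree. The blood draw is on that day's list, which ends with "Subjects will receive unified balanced evening meal". No fast is required before the draw, and nothing asks for fasting status to be recorded.

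**MAD Days 2 and 5 (12.2.4, 12.2.7).** "Subjects will be fasted from midnight (at least 10 hours fasting prior to dosing"; the dose is given between 07:00 and 09:00. The laboratory draw has no clock time and no pre-dose label.

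**MAD Days 8, 11 and 14 (12.2.10 to 12.2.12).** No fast is stated.

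**SAD Days 2 and 4 (12.1.4, 12.1.6).** Here the fast is tied to the laboratory sample: "Subjects will be fasted from midnight (at least 10 hours fasting prior to safety laboratory samples collection". For SAD Day -1, section 12.1.1 has morning arrival, while 8.1 and 12.1.2 have afternoon.

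**Time of day.** The end of protocol 12.4.1 says that collections scheduled by day, without a specific time, have no window but should generally be at the same time of day throughout.

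**The concern.** Glucose and triglycerides are in the chemistry panel (protocol Table 3), and both respond to meals. They also matter for this drug: protocol 8.3 reports effects on cholesterol and triglyceride levels in rats, and 6.1 describes oxythiamine as an inhibitor of sugar metabolism. Laboratory assessments are among the primary endpoint measures and are summarised by change from baseline (protocol 11.1, 14.8). Under 8.5.2 the safety review committee also looks at changes from baseline for trends.

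If the baseline is drawn under one set of conditions and later samples under another, the mean change within a cohort includes the difference in conditions. The study is uncontrolled, so no placebo group carries the same difference. The false component could imitate a drug effect, mask one, or make a follow-up value look like recovery.

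**Working it through.** **1. Is Day -1 really the baseline?** Table 5 gives 7 chemistry samples per MAD subject. Counting Table 2 visits: Screening, -1, 2, 5, 8, 11, 14 = 7. For the SAD part, Table 5 gives 5, and Table 1 gives Screening, -1, 2, 4, 8 = 5. Both match, so no further Day 1 draw is planned. Unless there is an unscheduled repeat, the last pre-dose value is Day -1.

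**2. Conditions at each MAD draw, as written.**

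| Draw | Time of day | Fast |
|---|---|---|
| Day -1 (baseline) | after afternoon arrival | none required |
| Days 2, 5 | not stated | overnight fast on that day, tied to dosing |
| Days 8, 11, 14 | not stated | none stated |

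The instruction to keep the time of day generally the same does not address fasting. It also fits poorly with an afternoon baseline if later draws are in the morning.

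The fasting sentence has its own inconsistency: midnight to 07:00-09:00 is 7 to 9 hours, short of the 10 hours it requires. The two must be reconciled.

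**3. Possible size.** The documents give no shift and no variance. Assumptions: triglycerides differ by 10-30% between the two conditions; within-subject CV is 22%, used as the SD on the log scale. The SAP uses absolute change; the log scale here is for illustration.

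- SD of one subject's log change = √2 × 0.22 = 0.311
- SE of the mean, n = 6: 0.311 / √6 = 0.127

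| Assumed shift | ln(1 + shift) | Shift / SE | Shift / SD of change |
|---|---|---|---|
| 10% | 0.095 | 0.75 | 0.31 |
| 20% | 0.182 | 1.4 | 0.59 |
| 30% | 0.262 | 2.1 | 0.84 |

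More subjects reduce the SE but leave the shift unchanged.

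**4. How often would it mislead?** With no drug effect and a baseline shift of b SDs of the change, the chance that a 95% interval for the mean change excludes zero comes from the noncentral t distribution with noncentrality b√n. For n = 6 it is 8% at b = 0.25, 17% at b = 0.5 and 51% at b = 1, against a nominal 5%. The assumed range of 0.31 to 0.84 SD lies between the first and last of these.

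**5. Do dose comparisons escape?** In 20,000 simulated pairs of cohorts of six sharing the same shift (0, 1 or 2 SD), the mean difference between cohorts was 0.000, -0.001 and 0.002, and a t-test rejected in 4.8%, 4.9% and 4.9%. A common shift cancels. A shift that differs between cohorts does not, and an effect shared by all doses stays confounded because there is no zero-dose group.

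**The case against.** The strongest reply is that the plan is silent rather than wrong.

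- A reader might infer that the baseline is unfasted. No document says so. Glucose carries a footnote mark in Table 3 whose text is not in the copy reviewed, and 12.3.5 refers to a laboratory manual with collection instructions that is not part of these documents. Either could address fasting. This stands: the accurate statement is that the visible text requires no fast. Triglycerides carry no footnote mark.
- A reader might infer that MAD Days 2 and 5 are fasted morning draws because they are listed before the dose. List order is not chronological: an examination timed at 4 hours post-dose is listed before the dose on both days. Table 2 footnote 4 requires results only before the Day 3 and Day 6 doses. This also stands, although lunch is about 4 hours post-dose (9.5), so a draw before lunch would still be fasted. The lack of timing is itself part of the problem.
- Safeguards exist. Actual values are tabulated, out-of-range values are flagged, the investigator judges clinical significance, and the safety review committee gives most weight to values outside normal ranges. These limit the harm to individual subjects but do not correct the mean change.
- Between-dose comparisons cancel a common shift. That is correct, but no such contrast is planned for laboratory data, and nothing standardises Day -1 conditions across cohorts.
- The study is descriptive and the issue concerns two analytes of a long panel. That is fair, and it limits the weight of the point.

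**Conclusion.** The point holds as a lack of standardisation. The MAD chemistry baseline follows afternoon arrival with no fast required, and no later draw is matched to it in writing, so within-cohort change in glucose and triglycerides can be confounded by meal and time of day.

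It should not be taken further. A reader might infer that the bias runs downward on treatment and hides a drug-related rise. That needs subjects to have eaten before the Day -1 draw and to be fasted on Days 2 and 5, and the documents establish neither; the rat findings in 8.3 are reported without a direction. Nor is there one mismatch across all visits, since Days 8, 11 and 14 carry no fasting rule. For the SAD part the arrival time is contradictory, so an afternoon baseline cannot be asserted there.

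The 0.75 to 2.1 standard errors at n = 6 rests wholly on the assumed 10-30% triglyceride shift and 22% CV. No figure is offered for glucose. The unmatched instructions are well established; the size of any bias is not. The change is worth making because it is cheap.

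**What to change.** **MAD part.**

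1. Keep the Day -1 sample for clearance to dose, so Table 2 footnote 4 is unaffected.
2. Add one fasted chemistry tube on Day 1, taken with the pre-dose PK sample, and define it in protocol 14.7 and SAP 6.2 as the baseline for chemistry.
3. State in 12.2 that the Day 2 and Day 5 laboratory samples are drawn pre-dose in the fasted state, and that the Day 8, 11 and 14 samples are fasted morning draws.
4. Reconcile fasting from midnight with the 10-hour minimum and the dosing window.

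**SAD part (completed).** Reconcile morning versus afternoon arrival on Day -1. Footnote the glucose and triglyceride change tables to say that fasting status at baseline was not standardised. The footnote should not call the baseline unfasted.

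**Cost.** One 5 mL tube: 242 + 5 = 247 mL per MAD subject, against the 500 mL cap in 8.6.4. Section 15.6.2 treats a change of up to two samples as non-substantial if the blood volume rises by no more than 50 mL. Beyond that, the cost is a fasting instruction for the later visits and a baseline sentence in each document.
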